For each subject, the final visit will usually be the preplanned SoC craniotomy/surgery at Visit 4. The subject will receive post-procedural management per institutional SoC. All ongoing follow-up and any further treatment will be in accordance with SoC and will not be recorded, including all medications and SoC procedure-related events occurring at and beyond Visit 4, and any SoC follow-up.

Subject-level standard of truth (SoT) will be defined by central histopathological diagnosis of the reference lesion. Lesion-level SoT will be defined by central histopathological diagnosis of all sampled lesions (reference lesions, MRI surgical lesions, additional PET lesions). Separately, central image analysis will define qualitative and quantitative lesion uptake of F-fluciclovine, for each resected lesion. These results will be reviewed by an Imaging Interpretation Committee to form image interpretation criteria.

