Subject-level diagnostic performance will be calculated based on reference lesion data, while lesion-level diagnostic performance will be calculated based on data of all sampled lesions.

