# 6.4.1.2 Secondary Efficacy Variables

Secondary efficacy endpoints include the following:

- Diagnostic performance (sensitivity, specificity, PPV and NPV) of different thresholds of quantitative and dynamic measures of lesion F-fluciclovine uptake versus SoT derived from central histopathological analysis of all lesions, at subject-level and lesion-level.
- Subject-level sensitivity, specificity, PPV and NPV of F-fluciclovine PET scan for detecting recurrent brain metastases, based on combined application of the established image interpretation criteria.
- Lesion-level sensitivity, specificity, PPV and NPV of F-fluciclovine PET for detecting recurrent brain metastases, based on combined application of the established image interpretation criteria.

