#### 7.4.3 Primary Efficacy Endpoint Analysis Methods

For each uptake threshold (Mild or Higher Uptake, Moderate or Higher Uptake, Marked Uptake), the number and percentage of True Positives, False Positives, True Negatives, and False Negatives will be presented for each reader. Sensitivity, Specificity, PPV and NPV will be calculated, with estimates and the 95% exact confidence intervals displayed.

The summary will be presented for subject-level performance (based on reference lesion data), and repeated for lesion-level performance (based on data of all sampled lesions).

For lesion-level performance, confidence intervals will be calculated based on the methodology described by Zhou et al., to account for clustering within subjects. The formula for PPV is:

$$\widehat{PPV} = \sum_{P} TP_{p} / \sum_{P} Pos_{p}$$

$$\widehat{Var}(\widehat{PPV}) = \frac{1}{P(P-1)} \sum_{P} \binom{Pos_{p}}{Pos}^{2} (\widehat{PPV_{p}} - \widehat{PPV})^{2}$$

With:

 $\boldsymbol{P}$ : (number of) Patients

 $\begin{array}{ll} p & : \text{ individual patient} \\ Pos_p & : \text{ Number of positive regions for patient } p \\ \hline Pos & : \text{ Number of true positive regions for patient } p \\ \hline Pos & : \text{ Number of true positive regions for patient } p \\ \hline Pos & : \text{ Mean cluster size} \end{array}$ 

 $\widehat{PPV_p} = TP_p/Pos_p$ : Patient PPV

The example in Zhou et al. is coded in SAS in Appendix 1.

In addition, pairwise inter-rater agreements at the lesion level for the 3 readers will be tabulated for the F-fluciclovine uptake. The proportions of agreement vs disagreement, Cohen's Kappa and the associated 95% confidence interval will be calculated.

Confidential Page 16 of 22 The results of these analyses will be reviewed by the separate Image Interpretation Committee as described in the study protocol to determine image interpretation criteria based on visual reads.

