# 7.4.4 Secondary Endpoint Analysis Methods

In order to establish other image interpretation criteria for  $^{18}\text{F}$ -fluciclovine PET in detecting recurrent brain metastases, receiver operating characteristic (ROC) analysis of SoT against the quantitative measures of lesion  $^{18}\text{F}$ -fluciclovine uptake will be performed for each reader. A ROC curve will be produced for lesion SUV $_{\text{max}}$ , SUV $_{\text{peak}}$ , TBR $_{\text{max}}$  and TBR $_{\text{peak}}$ , with each point corresponding to a specific threshold, eg.  $\geq$  SUV $_{\text{max}}$  value vs < SUV $_{\text{max}}$  value. The AUC of each curve will be calculated using the trapezoidal method and will be annotated on the plot. Sensitivity, specificity, PPV, and NPV will be listed for each value of lesion SUV $_{\text{max}}$ , SUV $_{\text{peak}}$ , TBR $_{\text{max}}$  and TBR $_{\text{peak}}$ .

For TBRmax and TBRpeak, pairwise inter-rater agreement will be assessed using Pearson correlation coefficients.

For dynamic measures of lesion F-fluciclovine uptake represented by TAC type, applying each TAC category as a diagnostic criterion, estimates and the 95% exact confidence intervals for sensitivity, specificity, PPV and NPV for each of the 4 TAC types will be calculated and presented, by reader, on both subject and lesion levels. Lesion-level confidence intervals will be based on the method by Zhou et al..

In addition, pairwise inter-reader agreements at the lesion level for the 3 readers will be tabulated for TAC type. The proportions of agreement vs disagreement, Cohen's Kappa and the associated 95% confidence interval will be calculated.

These analyses will be reviewed by the separate Image Interpretation Committee to determine a set of image interpretation criteria based on the quantitative and dynamic measures.

Subsequently, for the diagnostic performance secondary endpoints, estimates and the 95% exact confidence intervals for sensitivity, specificity, PPV and NPV will be calculated based on the recommended thresholds from the following combination of interpretation criteria (if featured in the interpretation criteria):

- 1. Visual assessment of level of lesion F-fluciclovine uptake
- 2. Strongest performing quantitative measure (based on ROC analysis)

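### SAP 7.4.4 gives the lesion-level combined-criteria endpoint exact intervals without the clustering exception stated for the other lesion-level intervals; these can be too narrow if many subjects contribute several lesions

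*SAP*

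**What the plan says.** SAP 6.4.1.2 lists two secondary endpoints for the combined criteria, one at subject level and one at lesion level. Both are "based on combined application of the established image interpretation criteria". Under SAP 6.4.1.1, "lesion-level diagnostic performance will be calculated based on data of all sampled lesions". SAP 6.1 takes the lesion-level truth from "central histopathological diagnosis of all sampled lesions (reference lesions, MRI surgical lesions, additional PET lesions", so one subject can supply more than one lesion.

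The interval method is stated in three places:

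- **Visual uptake (7.4.3).** The section opens with exact intervals ("with estimates and the 95% exact confidence intervals displayed"). For lesion level it then gives a between-subject variance formula "to account for clustering within subjects".
- **TAC type (7.4.4).** The order is the same: exact intervals first, then "Lesion-level confidence intervals will be based on the method by" the same cited textbook.
- **Combined criteria (last paragraph of 7.4.4).** "Subsequently, for the diagnostic performance secondary endpoints, estimates and the 95% exact confidence intervals for sensitivity, specificity, PPV and NPV will be calculated". No lesion-level sentence follows.

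The SAP gives no expected number of lesions per subject and no within-subject correlation. Section 7.6 plans up to 40 subjects without a formal calculation.

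**The concern.** An exact binomial interval takes every lesion as an independent observation. Lesions in one subject share the primary tumor, the treatment history and the scan, so their results may be positively correlated. The plan accepts this in two of its three lesion-level interval specifications and is silent in the third.

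Two things are at stake. First, the lesion-level interval for the combined criteria could overstate precision. Second, it would not be comparable with the visual and TAC lesion-level intervals: a difference in width would partly reflect the change of method, in either direction, and not only the added quantitative criterion.

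**Working it through.** The plan has no figure of its own to reproduce here: it states no interval width, event rate or correlation. The check therefore asks how far an exact interval goes wrong over a range of assumed clustering.

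**Inputs from the SAP.** Up to 40 subjects (7.6); 95% level; cluster variance from 7.4.3, which for P subjects with n_p lesions each and mean n̄ is

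Var = [1 / (P(P−1))] × Σ (n_p / n̄)² (p̂_p − p̂)².

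**Assumptions, not from the SAP.** True proportion 0.80; all 40 subjects in the denominator (a maximum, since sensitivity and specificity each use only part of the lesions); beta-binomial lesions; 3,000 runs per setting. The clustered comparator is a Wald interval, p̂ ± 1.96√Var, because 7.4.3 gives a variance but no interval form.

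**Design effect.** DE = 1 + ICC × (Σn² / Σn − 1), where ICC is the within-subject correlation. Example: if half the subjects have three lesions, Σn²/Σn = (0.5×1 + 0.5×9) / (0.5×1 + 0.5×3) = 5/2 = 2.5. At ICC 0.6, DE = 1 + 0.6 × 1.5 = 1.90.

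| Subjects with several lesions | ICC | DE | Exact: coverage, mean width | Clustered Wald: coverage, mean width |
|---|---|---|---|---|
| 10% with 2 | 0.3 | 1.05 | 96.6%, 0.249 | 93.5%, 0.240 |
| 10% with 2 | 0.6 | 1.11 | 95.5%, 0.249 | 92.6%, 0.245 |
| 25% with 2 | 0.3 | 1.12 | 96.0%, 0.232 | 92.8%, 0.231 |
| 25% with 2 | 0.6 | 1.24 | 94.2%, 0.234 | 92.8%, 0.244 |
| 50% with 2 | 0.3 | 1.20 | 95.4%, 0.213 | 92.9%, 0.219 |
| 50% with 2 | 0.6 | 1.40 | 92.3%, 0.212 | 92.3%, 0.236 |
| 50% with 3 | 0.3 | 1.45 | 91.1%, 0.184 | 91.8%, 0.208 |
| 50% with 3 | 0.6 | 1.90 | 87.3%, 0.182 | 91.9%, 0.237 |
| All with 3 | 0.6 | 2.20 | 83.0%, 0.149 | 93.1%, 0.211 |

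With 20 subjects and a quarter having two lesions, exact coverage was 97.1% at ICC 0.3 and 95.2% at ICC 0.6.

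**A second layout.** Take 28 subjects with 44 lesions: 16 with one, 8 with two, 4 with three. Then Σn² = 16 + 32 + 36 = 84 and Σn²/Σn = 84/44 = 1.909. DE runs from 1 + 0.3×0.909 = 1.27 to 1 + 0.8×0.909 = 1.73, so the true standard error is √1.27 = 1.13 to √1.73 = 1.31 times the binomial one. Exact coverage falls from 93.5% to 88.8% at a true 75%, and from 96.6% to 93.0% at 85%. With 34 lesions (22 with one, 6 with two) it stays at about 95% to 96%.

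**Does the 7.4.3 variance alone repair this?** Not as a Wald interval. At a true 85% and ICC 0.3 to 0.8:

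- 28 subjects, 34 lesions: exact 95.0–96.5%, clustered Wald 86.7–88.5%.
- 28 subjects, 44 lesions: exact 92.8–96.5%, clustered Wald 86.5–88.6%.
- 12 subjects, 20 lesions: exact 93.3–96.0%, clustered Wald 83.3–83.9%, with zero-width intervals in about 6–11% of runs.

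The same variance used on the logit scale with t quantiles, or in an exact interval at the effective sample size, covered about 95% to 99% in the settings tried.

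**The case against.** **The omission may be only editorial.** Exact intervals are the opening phrase in all three places and are twice overridden at lesion level, once within 7.4.4 itself. A dropped repeat of that convention is at least as likely as an intended switch. This stands as an explanation. It does not settle the text: 7.4.3 states the rule under the primary endpoint, and the plan thought it necessary to repeat it for TAC type. A programmer working from the last paragraph alone would produce exact intervals.

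**The harmful layouts are assumed.** Each subject has one reference lesion. MRI surgical lesions arise only if more than one equivocal lesion is intended for resection. Additional PET lesions must be discrete, neurosurgically feasible and planned for sampling (6.1). That may mean few multi-lesion subjects, where exact intervals hold their level and can even be wider than the clustered ones. This stands, and it limits the size of the point.

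**Little hangs on the interval.** The primary objective is visual criteria, whose lesion-level intervals are cluster-adjusted. The combined endpoint is secondary, there is no hypothesis test, and the SAP ties no decision to this interval. This also stands.

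**Copying the clustered method may not help.** That is right for a plain Wald interval, as the figures above show. It is a reason to name the interval form, not to leave the paragraph as it is.

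**Conclusion.** The inconsistency in the text is real. Read literally, the lesion-level combined-criteria intervals ignore clustering and differ in method from the plan's other lesion-level intervals.

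A reader might infer that these intervals are too narrow, or that the sponsor chose to ignore clustering. The SAP supports neither. It gives no lesions per subject and no correlation, so the most that can be said is that the intervals can be too narrow. Under the assumptions above, exact coverage is near or above 95% when few subjects have several lesions. It falls to roughly 84–89% with many multi-lesion subjects and high correlation, and lower still in the extreme case where every subject has three lesions.

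This is a modest point on a secondary estimate, worth correcting because the correction is cheap.

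**What to change.** Add to the last paragraph of SAP 7.4.4 that exact 95% intervals apply at subject level, and that lesion-level intervals use the cluster-adjusted variance of 7.4.3 in a named small-sample form. Two forms would serve:

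- a logit-scale interval with t quantiles; or
- an exact interval at the effective sample size, N / DE, with DE estimated as the cluster variance over the binomial variance.

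State a rule for estimates of 0% or 100%, where the cluster variance is zero. One option is an exact interval with the number of contributing subjects as the effective sample size. Do not use a plain Wald interval. Use the same form for the visual and TAC lesion-level intervals, or the methods will differ again.

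The cost is a few sentences and slightly more programming: Appendix 1 already codes the variance but stops before the interval. No new data are needed. The lesion-level intervals will often be somewhat wider.

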## 7.4.5 Statistical/Analytical Issues

#### 7.4.5.1 Handling of Dropouts or Missing Data

No imputations will be performed on missing data; all analyses will be based on observed data only.

7.4.5.2 Interim Analyses and Data Monitoring

Not applicable.

Confidential Page 17 of 22

#### 7.4.5.3 Multicenter Studies

This is a multicenter study, with approximately 10 sites expected to participate. Data collected from all study sites will be pooled for data analysis.

# 7.4.5.4 Multiple Comparisons/Multiplicity

There will be no adjustments for multiple comparisons in the efficacy analysis for this study.

#### 7.4.5.5 Examination of Subgroups

The summaries of different thresholds of lesion F-fluciclovine uptake, and time activity curve types, on visual reads vs standard or truth, at the lesion-level, will be repeated on the following subgroups:

Primary Tumor Type:

- Melanoma
- Breast
- Lung Cancer (NSCLC and SCLC)
- Gastrointestinal (Colorectal and Pancreatic)
- Genitourinary (Bladder, Kidney, Testes)
- Non-Lung/Breast/Melanoma

Concurrent Immunotherapy:

- Received Concurrent Immunotherapy
- Did Not Receive Concurrent Immunotherapy

Calculations will only be performed when there are at least 10 observations in the subgroup.

# 7.5 Safety Evaluation

Safety analysis will be carried out for the Safety analysis set, to include all subjects who have been dosed with IMP. Subjects who do not complete the study, for whatever reason, will have all available data up until the time of termination included in the analysis.

#### 7.5.1 Extent of Exposure

Each subject will receive a single dose of  $^{18}$ F-fluciclovine by injection, 185 MBq (5 mCi)  $\pm$  20%, delivered as an intravenous bolus by site staff. Total administered activity, in mCi and MBq, will be summarised, along with whether there were any injection site reactions during or immediately after dose, and if a dynamic PET/CT or PET/MRI scan was performed. Other details will be listed.

Confidential Page 18 of 22

#### 7.5.2 Adverse Events

Treatment-emergent adverse events (TEAEs) are defined as those AEs with onset after the dose of IMP, or existing events that worsened after the dose of IMP during the study, up to 1 day following IMP administration. Events reported with a partial onset date (e.g., month and year are reported but the day is missing) will be considered to be treatment-emergent if it cannot be confirmed that the event onset was prior to the dose of IMP based on the available date entries.

Adverse event verbatim terms will be coded to preferred terms and system organ classes using the latest version of MedDRA, version 23.0. Severity of AEs will be graded using the national cancer institute common terminology criteria for adverse events (NCI-CTCAE) v5.0.

Summaries that are displayed by system organ class (SOC) and preferred term (PT) will be ordered by descending incidence of SOC and PT within each SOC, and then alphabetically for SOC, and PT within SOC. Summaries of the following types will be presented:

- Overall summary of subject incidence of TEAEs by severity, relationship, and action taken, subject incidence of treatment-emergent serious adverse events (TESAEs) by relationship;
- Subject incidence of TEAEs by MedDRA system organ class and preferred term;
- Subject incidence of TEAEs by NCI-CTCAE grade, MedDRA system organ class, and preferred term;
- Subject incidence of TEAEs related to IMP by MedDRA system organ class, and preferred term;
- Subject incidence of TESAEs by MedDRA system organ class and preferred term.
- Subject incidence of TESAEs related to IMP by MedDRA system organ class and preferred term.

At each level of summarization (e.g., any AE, SOC, and PT), subjects experiencing more than one TEAE will be counted only once. For each subject and each adverse event, the worst severity recorded will be attributed and used in the by-severity summaries.

A by-subject listing of all adverse events (including non-treatment-emergent events) will be provided. This listing will include: subject identifier, age, sex, race, adverse event (SOC, PT, and verbatim term), date of onset and study day of onset, date of resolution and study day of resolution, duration, severity, seriousness, action taken, outcome and causality.

# 7.5.3 Deaths, Other Serious Adverse Events, and Other Significant Adverse Events

The following listings will be created:

Confidential Page 19 of 22

- A by-subject listing of all deaths that occurred during the study, including cause
- A by-subject listing of all serious adverse events

Listings will follow the format described for adverse events in Section 7.5.2.

#### 7.5.4 Clinical Laboratory Evaluation

Urine pregnancy test results will be listed.

### 7.5.5 Vital Signs

Vital signs recorded values and their respective changes from the pre-dose values will be summarized using descriptive statistics. All results will be listed.

#### 7.5.6 Concomitant Medications

Medications will be coded using WHODrug Global B3 Mar. 1, 2020.

Medications will be considered as prior medications and concomitant medications based on the following rules:

Medication Start date	Medication Stop date	Prior Medication	Concomitant Medication
Prior to date of IMP	Prior to date of IMP	Yes	No
Prior to date of IMP	On or after date of IMP	Yes	Yes
On or after date of IMP	Any	No	Yes

The following imputation rules will be used for determining prior/concomitant medications if the medication start or stop dates are incomplete:

- If medication start and/or stop dates are missing or partial, the dates will be compared as far as possible with the date of IMP. Medications will be assumed to be Concomitant only, unless there is clear evidence (through comparison of partial dates) to suggest that the medication started prior to the dose of IMP.
- If there is clear evidence to suggest that the medication started prior to the dose of IMP, the medication will be assumed to be both Prior and Concomitant, unless there is clear evidence to suggest that the medication stopped prior to the dose of IMP.
- If there is clear evidence to suggest that the medication stopped prior to the dose of IMP, the medication will be assumed to be Prior only.

All prior and concomitant medications will be listed by subject. Concomitant medications will be summarized by anatomical therapeutic chemical (ATC) Class (level 4) and generic drug name, using the safety analysis set. If level 4 is not

Confidential Page 20 of 22

available then level 3 will be used; if level 3 and 4 are not available then level 2 will be used.

Concomitant drug therapies relating to the treatment or corticosteroids for brain metastasis / lesions will be summarized separately, in the same way described above. The data will come from the Concomitant Medication and Cancer Drug Therapies eCRF page, and will include data with the indication for "Treatment for Brain Metastasis / Lesion" or "Corticosteroids for Brain Metastasis / Lesion".

## 7.6 Determination of Sample Size

Up to 40 subjects are planned for enrollment. The sample size is not calculated based on formal statistical hypothesis testing criteria, but is estimated to provide sufficient numbers of subjects and data to establish image interpretation criteria.

# 7.7 Changes in the Conduct of the Study or Planned Analyses

There were no changes to the study conduct or planned analyses identified within the development of this SAP, relative to the descriptions provided within the clinical study protocol.

## Appendix 1: SAS program to reproduce data in Zhou et al.

```
data one;
input TN
              No_Polyps;
Cards;
1
       1
2
       2
2
       2
1
       1
2
2
       2
1
       1
1
       1
1
       1
1
2
       2
0
       1
2
2
       2
1
       1
1
1
       1
2
       2
1
0
       2
1
       1
2
       2
2
       2
2
0
       1
;;;;
run;
proc sql;
   create table two as
      select
         TN,
         No_Polyps,
         TN/No_Polyps as Sei_hat,
         Se hat,
         No_Polyps/mNo as Ni_N,
         (calculated Ni N) * (calculated Ni N)
              * (calculated Sei hat-Se hat)* (calculated Sei hat-Se hat) as fc,
         sum(calculated fc) as sfc,
         calculated sfc/(n*(n-1)) as varSe_hat
      from
          (select
            sum(TN) as sTN,
            sum (No Polyps) as sNo,
            mean(No_Polyps) as mNo,
            count(*) as n,
            calculated sTN/calculated SNo as Se_hat
            from one ) as o,
         one;
quit;
data final;
   set two;
   if n = 1;
   keep Se hat varSe hat;
run;
```

Confidential Page 22 of 22
